8. ADVERSE EVENTS

[REDACTED]

[REDACTED]

[REDACTED].

8.1. Definition

8.1.1. Adverse Event

An adverse event (AE) is any untoward medical occurrence, unintended disease or injury, or untoward clinical signs (including abnormal laboratory findings) in subjects, users or other persons, whether or not related to the medical device under investigation.

Note 1: This definition includes events related to the medical device under investigation or the comparator.

Note 2: This definition includes events related to the procedures involved.

Note 3: For users or other persons, this definition is restricted to events related to medical devices under investigation.

8.1.2. Serious Adverse Event

If the AE meets any of the criteria below, it is regarded as a serious adverse event (SAE).

- a) Led to a death,
- b) Led to a serious deterioration in health of the subject, that either resulted in
 1. a life-threatening illness or injury, or
 2. a permanent impairment of a body structure or a body function, or
 3. in-patient hospitalization or prolongation of existing hospitalization, or
 4. medical or surgical intervention to prevent life threatening illness or injury or permanent impairment to a body structure or a body function.
 5. chronic disease
- c) Led to fetal distress, fetal death or a congenital abnormality or birth defect.

Note: A planned hospitalization for pre-existing condition, or a procedure required by the CIP, without a serious deterioration in health, is not considered to be an SAE.

8.1.3. Device Deficiency/Device Malfunction

Device deficiency is defined as an inadequacy of a medical device related to its identity, quality, durability, reliability, safety or performance, such as malfunction, misuse or use error and inadequate labeling. This includes the failure of the device to meet its performance specifications or otherwise perform as intended. Note: Performance specifications include all claims made in the labeling of the device.

A device malfunction is the failure of a device to meet its performance specifications or otherwise perform as intended, when used in accordance with the instructions for use or CIP.

8.2. Device Relationship

Determination of whether there is a reasonable possibility that an investigational product or device under investigation caused or contributed to an AE is to be determined by the **Investigator** and recorded on the appropriate CRF form. Determination should be based on assessment of temporal relationships, evidence of alternative etiology, medical/biologic plausibility, and patient condition (pre-existing condition).

8.2.1. Unanticipated (Serious Adverse) Device Effect [U(S)ADE]

Unanticipated serious adverse device effect (USADE) refers to any serious adverse effect on health or safety or any life-threatening problem or death caused by, or associated with, a device, if that effect, problem, or death was not previously identified in nature, severity, or degree of incidence in the investigational plan or application (including a supplementary plan or application), or any other unanticipated serious problem associated with a device that relates to the rights, safety, or welfare of subjects.

8.3.2. Determination of Adverse Events related to device and/or procedure

As detailed in Section 5.1, the primary endpoint of the study is to measure the safety and performance of Bitrack System. Among the ratios to be measured, the rate of death occurrence (SAE) during the surgery related directly to the use of the Bitrack System and the rate of any adverse event (AE) occurrence during the surgery directly related with the procedure and/or device under investigation will be determined.

8.3.3. Unanticipated Serious Adverse Device Effect Reporting to Sponsor and EC

The Sponsor requires the Investigator to report any USADE to the Sponsor within 24 hours of the investigator's knowledge of the event, unless local requirements are more stringent, and to the EC per EC requirements.

8.3.4. Device Deficiency/Malfunction Reporting

Clinical Sites	Reporting timelines
All Sites	
Device deficiencies/malfunctions must be reported to the Sponsor no later than 24 hours from the day the site personnel became aware of the event
 
[REDACTED]
 
[REDACTED]

Term	Percentage
GDP	100%
Inflation	100%
Interest rates	100%
Central bank	100%
Monetary policy	100%
Quantitative easing	100%
Inflation targeting	100%
Interest rate hike	100%
Interest rate cut	100%
Inflationary spiral	100%

CONFIDENTIAL
PL-PR01-027 A2

9. DATA AND DATA ANALYSIS: STATISTICAL CONSIDERATIONS

9.1. Analysis Populations

9.1.1. Intent-to-treat Population (ITT)

The intent-to-treat population (ITT) includes all adult humans derived for a robot assisted laparoscopic Radical/simple nephrectomy surgery using Bitrack System and its sterile endoscopic surgical instruments medical devices, in whom treatment using the device under investigation is attempted but not achieved.

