4.1. Clinical Investigation Procedures and Follow-up Schedule

The Clinical Investigation visits will occur as in-clinic visits at Baseline, Procedure, Discharge, 14 and 30-days follow-up.

The Flow Chart and the Follow-up phases of this clinical investigation are described in Figure 4-1 below.

[figure not shown]

Figure 4-1. Flowchart of the clinical investigation schedule

The scheduling of the clinical investigation visits will include the following:

Baseline visit (Visit 1)

During the baseline visit, the patient will be informed about the clinical study and provide signed informed consent form if surgeon decides that the patient is eligible as applicable. [REDACTED]
[REDACTED]
[REDACTED]
[REDACTED]

[REDACTED] In case of pregnancy, the patient will withdraw of the study a [REDACTED]
[REDACTED].

Procedure – (Visit 2)

The study population consists of subjects that provided signed ICF, met all inclusion criteria and none of the exclusion criteria, and successfully undergo surgery with the Bitrack System and its corresponding ESE/NESE instruments. These patients will be followed up until 30 days post-procedure. On the other hand, those subjects

in whom robot assisted laparoscopic radical/simple nephrectomy is attempted but not achieved will be followed-up for 30 days, but not included as population for analysis.

For research purposes, we will consider the start of the procedure at the moment of docking, meaning the moment when the camera of the robot is introduced inside the trocar. Therefore, all procedures that started but do not proceed with the use of the Bitrack system or are converted into a conventional laparoscopic/open surgery are included under the Intent-to-treat (ITT) population. Any robot assisted surgery converted to conventional laparoscopic/open surgery due to reasons different than the failure of the Bitrack System and its corresponding sterile endoscopic surgical instruments will be excluded from the endpoint analysis. █

This event will be considered a procedure failure.

CONFIDENTIAL
PI-PR01-027 A2

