5. ENDPOINTS

5.1. Primary Endpoint

The primary safety and performance endpoints of this early feasibility investigation are:

1. Evaluation of the safety of the Bitrack System by measuring the occurrence of Procedure-Related Adverse Events (PRAEs) and Serious Adverse Events (SAEs) during the procedure and through the 30 days post-procedure period of enrolled patients indicated for robot assisted laparoscopic radical/simple nephrectomy.
2. Evaluation of the performance of the investigational devices by means of its ability to access and reach the target zone, perform all relevant surgical tasks and to be withdrawn efficiently without conversion to MIS or open surgery. The performance of the Bitrack System and the ESE/NESE instruments will be analyzed through the conversion rate to conventional laparoscopy/open surgery.

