6.4. Subject Enrollment

For the HYROS study, a patient is considered enrolled in the clinical investigation from the moment they provide written informed consent, has been confirmed to meet all inclusion criteria and none of the exclusion criteria and has been successfully treated with the Bitrack System.

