9.1.2. Per-Protocol Population (PP)

Per-Protocol Population (PP) includes all subjects who fulfill the inclusion criteria, do not meet any exclusion criteria, have signed the informed consent form (ICF), and have undergone to a robotic assisted radical/simple nephrectomy surgery using Bitrack System medical device.

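### Section 9.1.1 defines the ITT as failed attempts only, so completed cases fall outside it and no set in 9.1 is explicitly all started procedures

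*Protocol*

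**What the plan says.** Section 9.1.1 describes the ITT as adults referred for robot-assisted radical or simple nephrectomy with Bitrack "in whom treatment using the device under investigation is attempted but not achieved". The sentence is complete and unredacted, and nothing in it brings in subjects whose treatment succeeded.

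Section 9.1.2 defines the per-protocol set as eligible, consented subjects who "have undergone to a robotic assisted radical/simple nephrectomy surgery using Bitrack System medical device". It does not say whether a converted case qualifies.

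Three other places bear on who is counted:

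- Section 4.1 (Procedure, Visit 2) sets the start of the procedure at docking and puts in the ITT "all procedures that started but do not proceed with the use of the Bitrack system or are converted into a conventional laparoscopic/open surgery". It also describes the study population as subjects who "successfully undergo surgery with the Bitrack System and its corresponding ESE/NESE instruments", and says that a subject in whom the operation "is attempted but not achieved will be followed-up for 30 days, but not included as population for analysis". Conversions for reasons other than failure of the system or its instruments are left out of the endpoint analysis.
- Section 6.4 counts a patient as enrolled only if, among other conditions, the patient "has been successfully treated with the Bitrack System".
- Section 5.1 says that device performance "will be analyzed through the conversion rate to conventional laparoscopy/open surgery". Neither 5.1 nor 9.2.1 names the analysis set for this rate. The safety endpoint refers to enrolled patients.

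**The concern.** An ITT set for a single-arm device study should hold every subject in whom use of the device was started, whatever the outcome. Section 9.1.1 does the reverse and keeps only the failures. If per-protocol is read as completed cases, the two populations are disjoint groups, failures and successes, rather than a full set and a subset of it.

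What is at stake is the denominator of the primary performance measure. A conversion rate needs converted and unconverted cases in the same set. A failures-only set cannot supply that. Adverse-event rates on it would describe failed operations and could not be read as rates for the device. If all operations succeed, the set is empty.

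Changing sections 4.1 and 6.4 so that failures are kept in the analysis would not by itself cure this, because 9.1.1 would still leave out the successes.

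**Working it through.** The protocol gives no rate, formula or sample-size calculation, so there is no figure to reproduce. The check is by enumeration.

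**Inputs**

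- Three subjects (sections 4 and 6.1.1).
- ITT = failed attempts (section 9.1.1).
- Enrolment requires successful treatment (section 6.4).
- Primary performance measure = conversion rate (section 5.1).
- f = number of failed attempts. Each failure is treated as a conversion. An attempt abandoned without conversion would be a failure but not strictly a conversion.

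**Started procedures.** Section 4 speaks of including three candidates, which points to three started. Section 6.1.1 fixes three enrolled, and 6.4 makes success a condition of enrolment. Together these could mean that operations continue until three succeed, so that 3 + f are started. Both cases are shown.

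**Formulas**

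- ITT as written: f/f
- All started, three started: f/3
- All started, three completed: f/(3 + f)

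| f | ITT as written | Three started | Three completed |
|---|---|---|---|
| 0 | 0/0, undefined | 0/3 = 0% | 0/3 = 0% |
| 1 | 1/1 = 100% | 1/3 = 33% | 1/4 = 25% |
| 2 | 2/2 = 100% | 2/3 = 67% | 2/5 = 40% |
| 3 | 3/3 = 100% | 3/3 = 100% | 3/6 = 50% |

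The ITT as written can give only 100% or no value. A successes-only set, which is what the study population of section 4.1 and the enrolment rule of section 6.4 describe, gives 0% by construction, or 0/0 if three are started and all fail. Neither can estimate a conversion rate.

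**Chance of an empty ITT.** With three started procedures and an independent failure probability p, the ITT is empty with probability (1 − p)³. The protocol gives no p, so these values are assumptions:

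- p = 5%: 0.95³ = 0.857
- p = 10%: 0.90³ = 0.729
- p = 20%: 0.80³ = 0.512
- p = 30%: 0.70³ = 0.343

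The better the device works, the more likely it is that the ITT holds nobody.

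**Does other text supply the missing set?** Section 4.1 says that procedures which "are converted into a conventional laparoscopic/open surgery are included under the Intent-to-treat (ITT) population". This could be read as adding failures to a wider set, but it does not say that completed cases belong there. In the same section, subjects described in the same terms as the 9.1.1 ITT are barred from analysis. The per-protocol wording might be stretched to cover a converted case in which Bitrack had been used, but it does not say so.

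**The case against.** The strongest reply is that the protocol never assigns an endpoint to the ITT. Sections 5.1 and 9.2.1 name no set, the safety endpoint refers to enrolled patients, and section 4.1 keeps failed attempts out of the analysis. Followed that way, the conversion rate is pushed towards 0%, not 100%. This stands. A reader might infer from 9.1.1 that the trial will report 100% conversion after a single failure. The documents do not support that, because it needs an ITT analysis that they nowhere specify.

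A second tempting inference is that every ITT rate is 100% by construction. It is not. That holds for the failure rate and, in practice, the conversion rate. AE and SAE rates among failed cases can take other values. Their fault is that they cover failed operations only and have no denominator when there are none.

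A third is that f/3 is simply the right rate. It assumes three started procedures, which sections 6.1.1 and 6.4 together leave open.

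It can also be said that 9.1.1 is a drafting slip. Section 4.1 fixes the start at docking and counts converted cases in the ITT, which suggests that a started-case set was intended. That is plausible, but no text states it.

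Finally, the study is exploratory, with three subjects and no hypothesis, and a reader given both failures and completed cases could rebuild the count. This lessens the practical harm. It does not remove the defect, because a descriptive rate still needs a valid denominator, and with three started cases one misplaced case moves the result by a third.

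**Conclusion.** The definition in 9.1.1 is wrong as written. It leaves out every completed case, no visible text puts them back, and no population in 9.1 is explicitly all started procedures.

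The numerical effect is conditional on computing the conversion rate on this ITT. With one failure, that rate would read 100% against 33% if three procedures are started, or 25% if three completed cases are required. With no failures it would not exist. These figures treat each failure as a conversion.

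The fault cannot be repaired in 9.1.1 alone. A corrected ITT would contradict section 4.1, which bars failed attempts and conversions not caused by the device, and section 6.4, which admits only successes to enrolment. These sections have to be settled together. A SAP could not settle the matter without overriding a definition that the protocol states.

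**What to change.** In one amendment:

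1. **Section 9.1.1.** Replace the restriction to failed attempts with all subjects in whom Bitrack treatment is attempted, whether or not achieved. Take the start as docking, as section 4.1 already does.
2. **Section 9.2.1.** Name this set for both primary endpoints. Keep per-protocol as a supplementary subset of it, and say in 9.1.2 whether a converted case qualifies.
3. **Section 4.1.** Reconcile with the new ITT the statement that failed attempts are not analysed and the exclusion of conversions for reasons other than device failure. Conversions can still be reported by cause within the full set.
4. **Section 6.4.** Remove the dependence of enrolment on successful treatment, so that the enrolled patients of the safety endpoint include failed attempts.
5. **Sections 4 and 6.1.1.** State whether the three subjects are started or completed cases.

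The cost is a wording amendment and its approval. Failed attempts are already followed for 30 days under section 4.1, so no extra patients, visits or data are needed.

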9.1.2. Per-Protocol Population (PP)

Per-Protocol Population (PP) includes all subjects who fulfill the inclusion criteria, do not meet any exclusion criteria, have signed the informed consent form (ICF), and have undergone to a robotic assisted radical/simple nephrectomy surgery using Bitrack System medical device.

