6.1.1. Number of Subjects

A total of 3 subjects will be enrolled in the clinical investigation.

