6.3.3. Exclusion Criteria

1. Pregnant or breastfeeding women at the time of the surgery
2. Inability to adhere to study-related procedures
3. Subject has known allergy to some of the device components (i.e., stainless steel, etc.)

CONFIDENTIAL
PL-PR01-027 A2

4. Subjects who participate in another trial which may affect the outcome data on this study or the ability to complete the follow up requirements
5. Subjects not suitable to undergo MIS/MIRS, according to medical criteria
6. Subjects with life expectancy inferior to 3 months
7. Subjects with a BMI ≥ 40 .
8. Subjects with severe cardiopulmonary or coronary artery disease, bleeding disorders or that have been submitted to multiple prior operations.
9. Subjects with abuses of active substances or with uncontrolled psychiatric disorders.
10. Subjects scheduled for surgeries intended to be in direct contact with the heart, the central circulatory system or the central nervous system.
11. Subjects with any contraindication for the use of the Bitrack System and the ESE/NESE instruments, as specified in the Instructions For Use

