9.2. Statistical Analyses

9.2.1. Primary Safety and Feasibility Endpoint Analyses

The primary safety and performance endpoints of this early feasibility investigation are:

- 1) Evaluation of the safety of the Bitrack System by measuring the occurrence of Procedure-Related Adverse Events (PRAEs) and Serious Adverse Events (SAEs) during the procedure and through the 14-days and 30-days post-procedure period of enrolled patients indicated for robot assisted laparoscopic Radical/simple nephrectomy surgery.

- 2) Evaluation of the performance of the investigational devices by means of its ability to access and reach the target zone, perform all relevant surgical tasks and to be withdrawn efficiently without conversion to MIS or open surgery.

Considering the low number of subjects, no formal hypothesis has been defined for this clinical investigation.

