9.3. Sample Size Calculation and Assumptions

HYROS is a feasibility study performed as an exploratory clinical investigation, to determine the limitations and advantages of Bitrack System, to capture information in order to freeze the design of the medical device and to progress to the validation stage. In this sense, only three patients are considered for this clinical investigation and consequently statistical considerations do not apply

This figure consists of a series of horizontal black bars of varying lengths, arranged in a grid-like pattern. The bars are positioned in rows, with some vertical spacing between the rows. The lengths of the bars vary significantly, with some being very short and others being very long, suggesting a wide range of values or categories. The bars are rendered in a solid black color and have a consistent thickness.

CONFIDENTIAL
PI -PR01-027 A2

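### A completed Bitrack case later found ineligible belongs to no analysis population, and the protocol leaves unclear whether that patient is enrolled and counted for safety

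*Protocol*

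**What the plan says.** The protocol describes who is analysed and followed in several places.

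- **Section 9.1.1, ITT:** patients referred for Bitrack nephrectomy "in whom treatment using the device under investigation is attempted but not achieved".
- **Section 9.1.2, PP:** "includes all subjects who fulfill the inclusion criteria, do not meet any exclusion criteria", have signed consent and have had the operation with the Bitrack System.
- **Section 4.1, study population:** consenting subjects who "met all inclusion criteria and none of the exclusion criteria, and successfully undergo surgery with the Bitrack System". They are followed for 30 days. Subjects in whom the operation was attempted but not achieved are also followed for 30 days.
- **Section 6.4, enrolment:** the patient has consented, "has been confirmed to meet all inclusion criteria and none of the exclusion criteria", and has been treated successfully with the device.
- **Section 6.3.1:** a patient who meets any exclusion criterion is excluded and may not be enrolled.
- **Sections 5.1 and 9.2.1, primary safety endpoint:** procedure-related and serious adverse events to 30 days in enrolled patients. No analysis population is named for it.
- **Sections 6.5 and 8.3.1:** enrolled subjects stay in until follow-up is complete, and safety surveillance starts at enrolment.

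The visible text defines no all-treated or safety population and gives no rule for a breach discovered after surgery.

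**The concern.** The two populations in section 9.1 do not between them cover everyone exposed to the device. One takes the unsuccessful cases and the other the eligible cases, so a successful but ineligible case falls between them. In a first-in-human study that patient's harms matter as much as anyone else's.

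The omission need not be neutral. Exclusion 8 includes "bleeding disorders or that have been submitted to multiple prior operations", with no requirement that the disorder be known beforehand. An intra-operative bleed could be both the adverse event and the discovery of the breach, so the patient with the harm would be the one whose place in the analysis is in doubt. Late findings are possible in other ways too: section 7.4 allows up to 4 weeks between baseline and surgery, and exclusion 1 refers to status at the time of surgery.

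**Working it through.** The protocol has no sample-size calculation to reproduce. Section 6.1.1 states "A total of 3 subjects will be enrolled in the clinical investigation", and section 9.3 says "only three patients are considered for this clinical investigation and consequently statistical considerations do not apply". The check is therefore a cross-classification of eligibility in fact against completion of the Bitrack operation, followed by an illustration of size.

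**Step 1: the four cases**

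| Eligible in fact | Bitrack surgery completed | ITT (9.1.1) | PP (9.1.2) | 30-day follow-up stated in 4.1 | Enrolled if 6.4 means eligible in fact | Enrolled if 6.4 means cleared before surgery |
|---|---|---|---|---|---|---|
| Yes | Yes | No | Yes | Yes | Yes | Yes |
| Yes | No | Yes | No | Yes | No | No |
| No | Yes | **No** | **No** | **No** | **No** | **Yes** |
| No | No | Yes | No | Yes | No | No |

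Only the third row is in neither population. It is also the only row without a follow-up sentence of its own in section 4.1, and the only row whose enrolment status depends on how section 6.4 is read.

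**Step 2: the two readings of section 6.4**

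*Stricter reading.* Section 6.3.1 bars enrolment when a criterion is met, not when a check has been failed. Section 6.4 also completes enrolment only after successful treatment, so a breach revealed during surgery comes before the moment of enrolment. The patient is then not enrolled, and the primary safety endpoint, the start of surveillance in 8.3.1 and the retention rule in 6.5, all of which refer to enrolled patients, do not reach the patient.

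*Lenient reading.* Section 6.4 speaks of eligibility that has been confirmed, which can mean the pre-operative check. The patient is then enrolled, 6.5 requires completion of follow-up, and the endpoint's wording includes the patient. Section 9.1 still offers no population that does.

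**Step 3: size, as an illustration**

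Assume that one treated patient is later found ineligible and is the only one with an event. The intervals are exact 95% (Clopper-Pearson). For x = 0 the upper limit is 1 − 0.025^(1/n), and for x = 1 the lower limit is 1 − 0.975^(1/n). The upper limit for x = 1 is the 0.975 quantile of Beta(2, n − 1).

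- All three treated patients counted: 1/3 = 33.3%. Lower limit 1 − 0.975^(1/3) = 0.8%; upper limit, from Beta(2, 2), 90.6%.
- That patient left out: 0/2 = 0%. Upper limit 1 − 0.025^(1/2) = 84.2%.
- That patient left out and replaced to reach three enrolled: 0/3 = 0%. Upper limit 1 − 0.025^(1/3) = 70.8%. Four patients have then been treated, and the all-treated result is 1/4 = 25.0% (0.6% to 80.6%).

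The chance of seeing at least one patient with an event is 1 − (1 − p)^n. The protocol gives no event rate, so p is assumed over a range, here independently of eligibility.

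| Assumed p | 3 patients counted | 2 patients counted |
|---|---|---|
| 5% | 14.3% | 9.8% |
| 10% | 27.1% | 19.0% |
| 20% | 48.8% | 36.0% |
| 30% | 65.7% | 51.0% |

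If the event itself prompts the exclusion, the loss is more selective than this table shows.

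**The case against.** The strongest reply is that a patient cleared before surgery and treated successfully satisfies section 6.4 even if the clearance later proves wrong. Sections 6.2.1 and 6.3.1 place the eligibility review at screening, on records and interview. On that view sections 6.5 and 6.6 carry the patient to the 30-day visit, the primary safety endpoint includes the patient, and the secondary endpoint covering all adverse events (section 5.2) has no enrolment qualifier at all. This reading is tenable. A reader might infer that such a patient is definitely not enrolled, has no follow-up and drops out of the primary safety endpoint. The documents do not support that as a firm statement. It holds only on the stricter reading, and parts of 4.1, 6.6 and 8.3.1 are redacted, so absence of a follow-up rule from the visible text cannot settle the matter.

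Three further objections also limit the point.

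- An allergy first revealed by a reaction during surgery might seem a second example. It is not one, because exclusion 3 requires a known allergy.
- A fall to 0/2 does not follow from non-enrolment, since three enrolled subjects are still called for; replacement would give 0/3.
- The study is small and exploratory: "Considering the low number of subjects, no formal hypothesis has been defined for this clinical investigation". The situation is uncommon, adverse-event data are fully source-verified (4.2.2), and serious events go to the sponsor within 24 hours (8.3.1).

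It can also be said that safety sets belong in a statistical analysis plan, which was not available here, and that limiting PP to eligible subjects is conventional. Both are fair. The fault is that this protocol does define its populations, and the definitions as written leave out an exposed patient.

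**Conclusion.** The point holds as a gap in the written definitions. A completed Bitrack case with a late-found eligibility breach is in neither ITT nor PP and is outside the section 4.1 study population, and sections 6.4 and 6.3.1 do not settle whether the patient is enrolled. On one reading the harms fall outside the primary safety endpoint. On the other they are inside its wording but have no analysis population, which leaves room to decide on inclusion once the outcome is known in an open-label, single-arm study.

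One such patient is a third of the planned data, and the reported safety result could change from one event to none. That rests on the assumption that the affected patient is the only one with an event; the protocol gives no basis for saying how likely this is. Severity is moderate: the scenario is uncommon and one reasonable reading retains the patient for safety, but the ambiguity can run in the direction of a cleaner result and is easily removed.

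**What to change.** 1. In section 9.1, define the population for primary endpoint 1 and the safety secondary endpoints as every consented subject whose procedure was started, using the docking definition already in section 4.1, whatever the surgical outcome and whatever is later found about eligibility. Keep PP as a supportive population.
2. In section 4.1, apply the existing 30-day follow-up to this whole group.
3. In section 6.4, state that a breach found after surgery is recorded as a deviation from the plan and does not remove the subject from safety follow-up or analysis. Align the wording of primary endpoint 1 in 5.1 and 9.2.1, and the start of surveillance in 8.3.1, with that statement.

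The cost is an amendment of wording. The number of planned subjects does not change and no new type of visit is added. The one downside for the sponsor is that the reported safety result may be slightly less favourable.
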